## **STUDY PROTOCOL**

### **1. Brief Summary of the Proposed Research**

This is a pilot randomized controlled trial of an intervention to improve arm function in children ages 6 to 17 with cerebral palsy and upper limb hemiparesis. Twenty participants will be randomized to either a group treated with neuromuscular electrical stimulation and video games or video games alone. Both groups will receive 6 wks of treatment. Changes in upper extremity motor impairment and function will be assessed for each participant at baseline, mid treatment, end of treatment and at 3 mo follow-up.

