### Methods and Procedures

Both the experiment group and control group interventions last 6 weeks and consists of therapist-guided sessions in the rehabilitation clinic and self-administered or caregiver-assisted sessions at home. While both groups will receive the same task practice and video game training, only the experiment group will receive an electrical stimulation device to assist with hand opening during practice. An adaptive randomization algorithm will be used to balance the two groups with respect to age, gender, and baseline severity (not severe if the child is Manual Activity Classification System level I-II, severe if level III-V). The treatment dose will be the same for both groups: 10 sessions per wk of self-administered video game training at home plus 2 lab sessions per wk for the first 3 wks and 1 lab session per wk for the final 3 wks – 58 hrs total. Blinded assessment of upper limb impairment and function will be done at baseline, mid-treatment, end-of-treatment, and 3-mos post-treatment.

- Note: Contralaterally controlled electrical stimulation (CCFES) – Enables patients with upper extremity hemiplegia to open their paretic hand by stimulating finger and thumb extensors with surface electrodes. Stimulation is proportional to degree of unimpaired hand opening as detected by an instrumented glove worn on the unaffected hand. Thus, volitional opening of the non-paretic hand produces stimulated opening of the paretic hand. CCFES is used during functional task practice and hand therapy video games to link motor intent with execution.
- Note: Hand Therapy Video Games – Four intuitive and engaging games were developed specifically for play with CCFES to provide goal-oriented motor skill training, impairment-appropriate difficulty, and performance feedback that motivates iterative play and skill improvement. Paddle Ball (i.e., Pong) is a simplified tennis simulation that uses hand movement to control a vertically moving paddle. Skee Ball uses hand-opening speed to launch balls at targets. Sound Tracker requires the

hand to precisely follow a moving track generated by different songs. Marble Maze uses hand opening to rotate mazes and guide marbles out into a bucket.

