Additionally, we will assess the following hand muscle co-activation measures during lab visits prior to treatment:

Intervention outcomes that are assessed at baselines, end of treatment, and follow up will include the following.

- Melbourne Assessment 2: This is an assessment of unilateral upper extremity function for children ages 2.5 to 15. Participants will perform 14 tasks using their weaker arm and hand, each of which is scored on a 3,4 or 5 point scale. The tasks involve using the hand to reach different positions (reaching, pronation, supination) and manipulate pellets and crayons. This assessment takes 15 minutes to perform.[9]
- Finger movement tracking accuracy: Finger movement tracking is a method of measuring motor control. Using the same bend sensor used for controlling the video games, the relative degree of finger extension will be displayed as a cursor on a computer screen, its vertical position corresponding to the degree of finger extension. A sinusoidal trace having a frequency of 0.1 Hz (1 cycle in 10 seconds) will scroll across the screen. The amplitude of the sine-wave track will be scaled so that it oscillates between 15% and 85% of the participant's full active finger extension. The participant will be seated with the wrist and forearm stabilized in a neutral posture. The participant's task is to keep the cursor on or as close to the scrolling trace as possible by extending and flexing their index finger. The vertical distance between the cursor and the target trace will be calculated for every time point of data collected. The final error for each 30-sec trial will be the average vertical distance (percentage of the participant's range of motion) from the cursor to the target trace. Three trials will be administered after a practice trial, resting 1 minute between trials. This test takes approximately 5 minutes.
- Box and Block Test: The Box and Block test is a measure of gross manual dexterity, which requires the participant to pick up 1 block at a time, move it over a partition, and release it in a target area as many times as possible in a 1-minute period. The Box and Block test measures changes in functional grasp and release but not during activities of daily living (ADL), and therefore cannot be strictly categorized as either an impairment or activity limitation measure. This test takes approximately 5 minutes.

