## **STATISTICAL ANALYSIS**

### **Sample size determination**

This is a pilot randomized control trial that aims to estimate the intervention effect necessary to power a larger trial. The sample size target of 20 participants was limited by the amount of funds provided by the R21 funding mechanism.

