### **Data analysis**

We will use a descriptive approach using means and standard errors to assess the effect of hand opening repetitions on the treatment group over time for each outcome. Due to the small sample size in our dataset, we will use a robust estimator to calculate the standard errors.

Upper extremity motor function will be assessed at enrollment, 6 weeks (end of treatment), and at 12 weeks post-treatment by a blinded assessor therapist. All assessments will be performed without any assistance from the stimulator and assessments will take place at least 24 hours after their last treatment session in order to avoid any transient carry-over effect or muscle fatigue. Change scores from the following outcomes will be calculated for each subject.

Descriptive statistics will be used to describe the results across patients and paired t-tests will be used to analyze the pre-post changes.

- Finger movement tracking error (squared sum distance from the target).
- Box and Block Test number of blocks successfully moved.
- Melbourne Assessment 2 percent score (0-100%).
- Assisting Hand Assessment score.

Additionally, adherence will be determined by downloading usage data from both the stimulator and the computer (via a portable USB thumb drive) – which will be used to calculate the percentage of prescribed treatment time completed by each participant. Participants will also be asked at every visit to report any difficulties or complications they may have experienced during home treatment sessions. Then, at the end of treatment, every participant will be interviewed regarding their impression of treatment and dosage, how easy or difficulty it was to use the equipment and play the games, and what changes they would suggest to the equipment or treatment dose, and whether or not they thought the treatment made any difference in their hand function. The number of hand opening repetitions will be recorded at each training session.

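### The sections disagree on whether a mid-treatment assessment takes place, none specifies its analysis, and the planned paired tests give no between-arm estimate

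*Combined protocol and SAP*

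**What the plan says.** Four places in the combined protocol and SAP state an assessment schedule.

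- Brief Summary: changes in impairment and function are "assessed for each participant at baseline, mid treatment, end of treatment and at 3 mo follow-up".
- Methods and Procedures: "Blinded assessment of upper limb impairment and function will be done at baseline, mid-treatment, end-of-treatment, and 3-mos post-treatment".
- Outcome Measures: "Intervention outcomes that are assessed at baselines, end of treatment, and follow up will include the following".
- Data analysis: "Upper extremity motor function will be assessed at enrollment, 6 weeks (end of treatment), and at 12 weeks post-treatment".

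For the analysis, the plan says that "paired t-tests will be used to analyze the pre-post changes", applied to change scores for four outcomes: finger tracking error, Box and Block, Melbourne Assessment 2 and Assisting Hand Assessment. It also plans a descriptive summary using "means and standard errors to assess the effect of hand opening repetitions on the treatment group over time for each outcome". No rule for missing scores is given. On sample size, "The sample size target of 20 participants was limited by the amount of funds provided by the R21 funding mechanism".

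**The concern.** Two sections include a mid-treatment assessment and two leave it out. Whichever schedule staff follow, they depart from half of the document. If practice varies between children, a 20-child data set becomes uneven.

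The visit also cannot be run as written. Its week is not stated, and neither are the tests to be given. Data analysis asks for at least 24 hours between the last treatment session and any assessment. Methods and Procedures schedules ten home sessions a week plus lab sessions. The two can be compatible, but nothing says how a test in the middle of treatment would be fitted in.

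The analysis raises a further problem. The trial exists to estimate how much the stimulation adds to video games alone, and to supply that effect for a larger trial. A paired pre-post test describes change within children. It does not estimate the difference between arms, and it leaves out any child without the later score, even if that child was assessed at another post-baseline visit. A fourth time point with no stated analysis also leaves room for selective reporting.

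**Working it through.** **1. The four schedules side by side**

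| Section | Baseline | Mid-treatment | End of treatment | Follow-up |
|---|---|---|---|---|
| Brief Summary | yes | yes | yes | 3 months |
| Methods and Procedures | yes | yes | yes | 3 months |
| Outcome Measures | yes | not listed | yes | yes |
| Data analysis | yes | not listed | yes (6 weeks) | 12 weeks |

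Three months and 12 weeks agree approximately, so mid-treatment is the only time point in conflict. All four statements are current text.

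**2. Count of assessments.** N = 20 (Sample size determination). Four time points: 20 × 4 = 80 participant-assessments. Three time points: 20 × 3 = 60. The difference is 20 visits.

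**3. Assessor time for the disputed visit.** The test durations are in Outcome Measures: Melbourne Assessment 2, 15 min; tracking, 5 min; Box and Block, 5 min; Assisting Hand Assessment, 15–20 min.

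- All four tests: 15 + 5 + 5 + 15 to 20 = 40–45 min. Over 20 children this is 800–900 min, or 13.3–15 hours.
- Tracking and Box and Block only: 5 + 5 = 10 min. Over 20 children this is 200 min, or 3.3 hours.

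Which tests are given is an assumption, so the range is about 3–15 hours.

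**4. What the visit adds to the end-of-treatment arm difference.** The documents give no correlations and no allocation ratio. I assume an equal correlation ρ between any two visits, ρ = 0.5–0.8, and 10 children per arm.

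- Complete data: each child's end-of-treatment score is observed. In a model with arm, visit, arm-by-visit and baseline score, the mid-treatment score then adds essentially nothing to the end-of-treatment contrast.
- Dropout after mid-treatment: given baseline, the correlation between the mid and end scores is r = (ρ − ρ²)/(1 − ρ²) = ρ/(1 + ρ). A child with a mid-treatment score only recovers a fraction r² of the information lost. If a fraction d = 1/10 of each arm leaves after that visit, the large-sample variance of the contrast falls by about d × r².

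| ρ | r = ρ/(1 + ρ) | r² | 0.1 × r² |
|---|---|---|---|
| 0.5 | 0.333 | 0.11 | 1.1% |
| 0.7 | 0.412 | 0.17 | 1.7% |
| 0.8 | 0.444 | 0.20 | 2.0% |

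**5. Sample size.** N was set by funding, and no power inputs are stated, so there is no planned figure to reproduce and none that depends on this visit.

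**The case against.** The strongest reply is that this is a wording slip in a small, funding-limited pilot. Baseline, end of treatment and follow-up appear in all four sections, the pre-post tests need no mid-treatment value, and N does not depend on it. All of that stands. Taken alone, the schedule mismatch is close to an editorial correction.

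It can also be said that the repeated-measures model addresses a different gap, the missing between-arm comparison. That is partly right. The two belong together because any decision on the visit has to say how its data will be used, and the listed paired tests have no place for it. With 20 children the model does bring covariance and small-sample assumptions that a paired t-test avoids.

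Three stronger readings are tempting and should be resisted.

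- *Mid-treatment data would be collected and then discarded.* The text does not say this. The descriptive summary over time does not itemise its time points and could include mid-treatment, although the same section lists only three assessments. What can be said is that no analysis is specified.
- *The extra visit would cut variance by 13–17%.* That holds only for an effect averaged over visits. The baseline-adjusted variance of the mean of m post-baseline visits is (1 + (m − 1)ρ)/m − ρ². Going from m = 2 to m = 3, it falls from 0.50 to 0.417 at ρ = 0.5 (17%), and from 0.26 to 0.227 at ρ = 0.8 (13%). It does not apply to the end-of-treatment contrast. If the mid-treatment effect were only half the later one (an assumption), the averaged effect would fall to (0.5 + 1 + 1)/3 = 0.83 of its size, which would outweigh the smaller standard error.
- *The visit costs 13–15 assessor hours.* This assumes that all four tests are given, which no section states.

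**Conclusion.** The contradiction is exact and unresolved: two sections schedule the mid-treatment assessment, two omit it, and none gives its week, outcomes or analysis. It does not invalidate the trial. The planned pre-post tests and the sample size are unaffected.

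The more useful part of the point is the analysis. The paired tests lose children without the later score and leave the between-arm effect unestimated, although the Specific Aims turn on it. With an assumed 10 per arm, each lost child is a tenth of an arm.

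Precision is not a reason to keep the visit. Its gain for the end-of-treatment contrast is negligible with complete data and only 1–2% in the dropout case worked above, under equal correlations and a large-sample formula. The decision should rest on whether early response is of interest and whether the assessment time is acceptable.

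**What to change.** 1. Reconcile the four sections. Either delete mid-treatment from the Brief Summary and Methods and Procedures, or add it to Outcome Measures and Data analysis with its week and the outcomes measured.
2. In either case, analyse all post-baseline visits that are collected in one repeated-measures model per outcome, with arm, visit, arm-by-visit and baseline score. Include every child with at least one post-baseline score.
3. Name the end-of-treatment arm difference, with its confidence interval, as the main contrast. State the covariance structure in advance and use a small-sample degrees-of-freedom correction. The paired pre-post summaries can stay as description.

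The cost is protocol and SAP wording, slightly more analysis work, and reliance on modelling assumptions that 20 children can check only weakly. No visit is added beyond those that the Brief Summary and Methods and Procedures already promise. If the mid-treatment visit is deleted, a child who leaves before the end-of-treatment assessment and has no follow-up score cannot contribute to the model.

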### **Rationale**

Cerebral palsy is the leading cause of disability in children, one third of whom suffer from hemiparesis. Video games and functional electrical stimulation are complimentary approaches that have independently improved outcomes in hemiplegic cerebral palsy children [1], [2]. We propose a unique intervention that combines custom hand therapy video games with contralaterally controlled functional electrical stimulation (CCFES). CCFES assists hemiparetic children to open their paretic hand in direct proportion to the degree of voluntary unimpaired hand opening, as detected by a sensor glove worn on the child's unimpaired hand. This is designed to facilitate motor control learning by linking movement intent to motor execution and returning somatosensory and proprioceptive sensations back to the brain.

In order to facilitate exercise with CCFES at home, we developed finger-motion controlled video games that are played with the assistance of CCFES. The video games are played by opening and closing the paretic hand, and facilitate motor practice based on learning principles (goal-oriented movement, intense repetition, task variation, engagement and motivation, and appropriate task difficulty). The finger motions are captured by a sensor that is attached to a fingerless glove worn on the paretic hand.

Because hand therapy video games without CCFES assistance may also be an efficacious therapy in this population, we propose a randomized clinical study comparing CCFES + video games to video games without CCFES.

This will be the first controlled trial of the CCFES + Video Game treatment in cerebral palsy. The purpose of the study is to estimate its efficacy in improving arm/hand movement and function.

### Specific Aims

The primary aim of this study is to collect pilot data to estimate the efficacy of CCFES videogame therapy in improving outcomes of upper extremity impairment and function. CCFES + videogame therapy is new, so estimating its effect is a first step to test our hypothesis that it leads to greater outcomes than video game therapy alone. We will assess clinical measures of upper extremity impairment, function, and community use to test this hypothesis.

### Methods and Procedures

Both the experiment group and control group interventions last 6 weeks and consists of therapist-guided sessions in the rehabilitation clinic and self-administered or caregiver-assisted sessions at home. While both groups will receive the same task practice and video game training, only the experiment group will receive an electrical stimulation device to assist with hand opening during practice. An adaptive randomization algorithm will be used to balance the two groups with respect to age, gender, and baseline severity (not severe if the child is Manual Activity Classification System level I-II, severe if level III-V). The treatment dose will be the same for both groups: 10 sessions per wk of self-administered video game training at home plus 2 lab sessions per wk for the first 3 wks and 1 lab session per wk for the final 3 wks – 58 hrs total. Blinded assessment of upper limb impairment and function will be done at baseline, mid-treatment, end-of-treatment, and 3-mos post-treatment.

- Note: Contralaterally controlled electrical stimulation (CCFES) – Enables patients with upper extremity hemiplegia to open their paretic hand by stimulating finger and thumb extensors with surface electrodes. Stimulation is proportional to degree of unimpaired hand opening as detected by an instrumented glove worn on the unaffected hand. Thus, volitional opening of the non-paretic hand produces stimulated opening of the paretic hand. CCFES is used during functional task practice and hand therapy video games to link motor intent with execution.
- Note: Hand Therapy Video Games – Four intuitive and engaging games were developed specifically for play with CCFES to provide goal-oriented motor skill training, impairment-appropriate difficulty, and performance feedback that motivates iterative play and skill improvement. Paddle Ball (i.e., Pong) is a simplified tennis simulation that uses hand movement to control a vertically moving paddle. Skee Ball uses hand-opening speed to launch balls at targets. Sound Tracker requires the

hand to precisely follow a moving track generated by different songs. Marble Maze uses hand opening to rotate mazes and guide marbles out into a bucket.

- i. Rehabilitation clinic sessions – These will occur up to twice per week for the first 3 weeks and once per week for the second 3 weeks of the 6 week treatment. They are therapist-guided and last up to 90 min consisting of 45 minutes of CCFES-mediated video games and up to 45 minutes of CCFES-mediated functional task practice. Early sessions will focus on training the patient and caregiver to self-administer play of a CCFES-mediated video game at home. As proficiency with one game develops, more games will be introduced. The functional task practice part of the session will engage the participant in using the CCFES system to assist them in practicing using their hand in activities such as lacing beads, throwing balls, eating finger foods, and other play and activities of daily living.
- ii. Home sessions – These consist of CCFES-mediated hand opening and video game exercises with caregiver assistance and supervision as needed. As proficiency develops and more games are added, each home session will increase in duration up to 90 minutes per day, as determined by the treating therapist based on the adherence of each participant. Self report of game difficulty and engagement will be made at the completion of each game (see below)

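### The analysis uses raw change scores and paired t-tests, with neither the baseline score nor the balancing factors as covariates, although the aim is a between-arm estimate from 20 children

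*Combined protocol and SAP*

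**What the plan says.** All references are to the combined protocol and SAP.

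- **Aim.** Sample size determination says that the trial "aims to estimate the intervention effect necessary to power a larger trial". Specific Aims states the hypothesis as superiority over video games alone. The quantity of interest is therefore a difference between arms.
- **Design and size.** "Twenty participants will be randomized to either a group treated with neuromuscular electrical stimulation and video games or video games alone" (Brief Summary). The allocation ratio is not stated. "The sample size target of 20 participants was limited by the amount of funds provided by the R21 funding mechanism", so there is no power calculation, SD or correlation to work from.
- **Balancing.** "An adaptive randomization algorithm will be used to balance the two groups with respect to age, gender, and baseline severity" (Methods and Procedures). Severity is split at Manual Ability Classification System (MACS) levels I-II versus III-V.
- **Baseline data.** "Intervention outcomes that are assessed at baselines, end of treatment, and follow up will include the following" (Outcome Measures).
- **Analysis.** "Change scores from the following outcomes will be calculated for each subject", and "paired t-tests will be used to analyze the pre-post changes" (Data analysis). The outcomes are tracking error, Box and Block, Melbourne Assessment 2 and Assisting Hand Assessment. No covariate is named, and no between-arm contrast is defined.
- **Standard errors.** "Due to the small sample size in our dataset, we will use a robust estimator to calculate the standard errors". This sits in the paragraph on hand-opening repetitions. The type of estimator is not given, nor whether it extends to the change scores.

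**The concern.** The trial measures each outcome before treatment and balances the arms on three factors, presumably because the sponsor thinks them prognostic. The analysis then makes limited use of this information. A change score fixes the coefficient of the baseline at 1, whereas a regression estimates it. Age, gender and MACS severity do not enter at all.

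With the sample fixed by funding, the analysis is where precision can still be gained, and the estimate with its uncertainty is what the larger trial will be built on. Chance imbalance matters too. Balancing a two-level MACS split does not equalise the baseline score of each outcome, and in a change-score contrast any baseline difference carries through in proportion to one minus the baseline-to-follow-up correlation.

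**Working it through.** The plan has no calculation to reproduce, because 20 is a funding limit.

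**Inputs.** N = 20 (Sample size determination). Assumed: 10 per arm, complete data, equal outcome variance at baseline and follow-up, and the correlation rho between them. Results are in units of the outcome SD.

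**1. Baseline adjustment alone.** The variance per child is 2(1 − rho) for a change score and 1 − rho² for ANCOVA, a ratio of (1 + rho)/2. The half-width is t × √(2 × variance/10). The ANCOVA variance is multiplied by 1 + 1/16 for chance baseline imbalance. The t values are 2.101 (18 df) and 2.110 (17 df).

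| rho | Change score | ANCOVA, baseline only | Ratio |
|---|---|---|---|
| 0.5 | 2.101 × √0.200 = 0.940 | 2.110 × √(0.150 × 1.0625) = 0.842 | 0.90 |
| 0.7 | 2.101 × √0.120 = 0.728 | 2.110 × √(0.102 × 1.0625) = 0.695 | 0.95 |
| 0.9 | 2.101 × √0.040 = 0.420 | 2.110 × √(0.038 × 1.0625) = 0.424 | 1.01 |

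**2. Chance imbalance.** Under simple randomisation the between-arm baseline difference has SD √(2/10) = 0.45; balancing on MACS reduces this only in part. At rho 0.5, a difference of 0.45 SD shifts a change-score contrast by (1 − 0.5) × 0.45 = 0.22 SD.

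**3. Adding the balancing factors.** This was simulated with 3,000 trials per setting, N = 20 and no treatment effect. Allocation was by minimisation on three binary factors, taking the better-balancing arm with probability 0.8. MACS was assumed to explain 30% of baseline variance and to act on follow-up only through baseline. Age and gender together explained either none or 30% of the follow-up variance left after baseline. The full model has arm, baseline and three factors (14 df).

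| rho | Age and gender share | Unadjusted contrast: reported SE vs true SD | Half-width, change score | Half-width, full model |
|---|---|---|---|---|
| 0.5 | none | 0.441 vs 0.434 | 0.926 | 0.875 |
| 0.7 | none | 0.342 vs 0.344 | 0.718 | 0.716 |
| 0.9 | none | 0.197 vs 0.202 | 0.413 | 0.440 |
| 0.5 | 30% | 0.445 vs 0.398 | 0.935 | 0.733 |
| 0.7 | 30% | 0.344 vs 0.313 | 0.724 | 0.605 |
| 0.9 | 30% | 0.200 vs 0.178 | 0.421 | 0.370 |

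In the 30% rows the reported SE of an unadjusted contrast is 10 to 12% too large (for example 0.445/0.398 = 1.12), and type I error is 2.3 to 3.2% instead of 5%. In the rows with no share the SE is about right. There, the baseline-only model had half-widths of 0.825, 0.678 and 0.415, so adding three uninformative factors cost about 6% in width (0.875/0.825 = 1.06).

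**4. Choice of standard error.** With an uncorrected sandwich estimator (HC0) and normal critical values, type I error was 7 to 8.5% for the unadjusted contrast when age and gender explain nothing, and 12 to 14% in the full model. With model-based SEs and t critical values the full model stayed at 4.7 to 5.5% for these three correlations. HC3 was not simulated.

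**The case against.** The strongest reply is that covariate choice is secondary: the plan has no between-arm analysis at all, and that is the larger gap. This is true. But adding an unadjusted change-score contrast would leave the inefficiency in place, so the covariates should be settled when the contrast is written.

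A reader might go further than the documents allow in four ways.

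- **That the planned standard errors are overstated.** The paired t-test is a within-child comparison, and its SE is not inflated by ignoring balance between arms. The 10 to 12% figure belongs to an unadjusted between-arm contrast that the plan does not contain, and it arises only if the factors are prognostic. An unspecified robust estimator could err in the opposite direction.
- **That the baseline is ignored.** It is used, by subtraction. What is missing is its use as a covariate.
- **That full adjustment is certain to help.** If age and gender explain nothing, the four-covariate model gains little at rho 0.5, nothing at 0.7, and is about 6.5% wider at 0.9 (0.440/0.413). The fact that the sponsor chose these factors suggests that they are thought prognostic, but does not show it.
- **That the SD handed to the larger trial would be too large.** The SD of change is the right input if that trial analyses change scores, and the residual SD if it uses ANCOVA. The documents do not say which it will use.

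These objections limit the size of the gain and the number of covariates. They do not remove the case for baseline adjustment.

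**Conclusion.** The point holds as one of efficiency and pre-specification; it does not show that the planned tests are invalid. The Data analysis section enters no covariate, although the between-arm effect is the trial's product and the baseline scores and balancing factors are already collected.

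Adjusting for baseline alone shortens the between-arm interval by about 10% at rho 0.5 and 5% at rho 0.7, and costs about 1% at 0.9. Adding the balancing factors ranges from a clear gain (0.935 to 0.733 SD at rho 0.5 with a 30% share) to a small loss (0.413 to 0.440 SD at rho 0.9 with none). All of this assumes 10 per arm, and the correlations and prognostic shares are assumptions. The case for the baseline covariate is therefore firm, and the case for each further factor is conditional.

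**What to change.** In the Data analysis section, for each outcome and post-baseline visit:

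- Estimate the CCFES-minus-control difference from a linear model of the follow-up score on arm and that outcome's baseline score.
- Add the balancing factors, pre-specified and kept few, with MACS severity (I-II versus III-V) first. State the form in which age enters. If any factor is left out, say which and why before the data are seen. The simulation does not test this order, because it lets MACS act only through baseline.
- Use a model-based or HC3 standard error with t critical values, in place of an unnamed robust estimator.
- Report the difference with its 95% CI, and keep within-arm changes as description.
- Report the residual SD and the baseline-to-follow-up correlation, so that the larger trial can be sized for either form of analysis.

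The cost is SAP wording; no new data are needed. With all four covariates the residual df fall from 18 to 14 and the t critical value rises about 2% (2.145/2.101). If the factors are not prognostic the interval may be slightly wider than that of a change-score contrast.
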